2.5. Study Design

This FIH/FIP study is an open-label, multi-center, ascending dose study designed to evaluate the safety and tolerability of a single IV infusion of fordadistrogene movaparvovec in

participants with DMD. There are 22 participants who received a single dose of fordadistrogene movaparvovec between 1E14 vg/kg and 3E14 vg/kg per the ITR-based method or 2E14 vg/kg per the TG-titer method.

Fordadistrogene movaparvovec at 3E14 vg/kg per the ITR-based titer method is approximately equivalent to 2E14 vg/kg per the TG-titer method. Therefore, participants dosed at 3E14 vg/kg per the ITR-based titer method or at 2E14 vg/kg per the TG-titer method will be grouped in the high dose cohort.

- 1. Ambulatory low dose cohort (N=3): 1E14 vg/kg based on the ITR method
- 2. Ambulatory high dose cohort (N=16): 3E14 vg/kg based on the ITR method or 2E14 vg/kg based on the TG method
- 3. Non-ambulatory high dose cohort (N=3): 2E14 vg/kg based on the TG method
 - Sirolimus non-ambulatory high dose cohort (N=1): 2E14 vg/kg per the TG-based titer method.

Note that a safety profile will be provided for the one participant who received sirolimus. No other summaries will be provided since only one participant received sirolimus.

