5. GENERAL METHODOLOGY AND CONVENTIONS

5.1. Hypotheses and Decision Rules

There is no formal hypothesis testing in this study according to the original design of this FIH study. Because the study has a relatively small sample size and is not designed to have sufficient power to detect treatment differences, it is expected that hypothesis testing is not likely to reach statistical significance unless there is dramatic treatment effect. Nominal p-values will be presented. The 95% CI for the change from baseline in secondary (dystrophin expression/distribution)

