5.2. General Methods

the subgroup.

Bootstrap to estimate the parameter of interest

Given the relatively small sample size of this study and the variability of the various outcome parameters, the non-parametric bootstrapping method (Efron 1979², Efron 1993³) will be used to compute the $100(1-\alpha)$ % CIs of the parameters of interest for robust evaluation without underlying distributional assumptions. Specifically, the sampling distributions of the statistics derived from 10,000 bootstrap samples such as the mean of the change from baseline in an endpoint will be used to construct the 95% CI of the mean when $\alpha = 0.05$.

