6.2.2. Mini-dystrophin/Dystrophin Distribution by Immunofluorescence

Endpoints:

- Percent of dystrophin and mini-dystrophin positive muscle fibers derived from the individual fiber MSD data, measured by immunofluorescence assay using DYSB antibody (IF DYSB)
- Percent of mini-dystrophin positive muscle fiber derived from the individual fibers MSD data, measured by immunofluorescence assay using mini-dystrophin specific antibody (IF mini-dys)

The analyses listed below will be performed for each of the 2 endpoints. The analyses will be performed using the Pharmacodynamic Analysis Set. Presentations will include:

• Raw values, change from baseline and % change from baseline will be summarized descriptively by dose cohort, ambulatory status at baseline, and study visit.

- A boxplot (for cohort(s) with over 3 participants, data points display only for cohort with ≤3 participants) presenting the distribution of the change from baseline against study visit. A similar plot will also be generated for raw values and % change from baseline.
- An individual plot presenting raw levels against study visit, paged by dose cohort and ambulatory status at baseline. A similar plot will also be generated for the change from baseline.

Determination of % positive fibers from the immunofluorescence assay (DYSB and minidystrophin specific antibody):

The primary variables include the percent of positive fibers, the total number of fibers, and the percent of non-muscle tissue in biopsy. The determination of percent positive fibers is summarized as follows:

- Biopsy samples in stained slides will be sent to an independent vendor for processing. The digital image of each slide is generated.
- An ROA is outlined by pathologists in a platform.
- Each fiber membrane is scanned using a scanner. The whole biopsy quantitation of dystrophin mean myofiber MSD is determined for each fiber within the ROA. These data are called the individual fiber MSD data.
- The fiber MSD value for each fiber in the ROA is compared to a positive fiber threshold value to determine the number of fibers exceeding the threshold value within the ROA for each slide. The percent of positive fibers is computed as the number of positive fibers divided by the total number of fibers for each slide.

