For each participant, the individual baseline fiber MSD method will be used to determine the threshold for positive fibers to better characterize the individual change from baseline. The distribution of the individual fiber MSD data will be examined and plotted. The 95th percentile of the baseline fiber MSD distribution for each slide obtained prior to dosing will be computed. The maximum of the 95th percentiles obtained from the baseline distribution(s) will be used as the threshold for positive fibers. This individual threshold of staining density will be established for each participant such that at least 95% of fibers have a staining density below the threshold for each slide analyzed at baseline.

For the newly developed mini-DYS/Laminin Image Analysis assay, a global threshold for calculating the percentage of mini-dystrophin positive fibers will be established based on all baseline samples from the 19 ambulatory participants. The quantification of the immunofluorescence intensity level (MSD) associated with the individual muscle fibers will be used to calculate the 99th percentile of the overall fiber MSD distribution. The

[figure not shown]
corresponding fiber MSD threshold value will be determined. Any muscle fiber with an MSD value above this calculated threshold value will be considered as a positive fiber.

[figure not shown]
At each scheduled visit of muscle biopsy, the average of the percent of positive fibers obtained in each slide will be computed. This percent of positive fibers will be summarized by dose cohort and ambulatory status at baseline. Key fiber MSD distribution statistics including the mean and the median will be summarized. In addition, non-parametric Wilcoxon test will be used to examine the change in fiber MSD distributions.

[figure not shown]

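### SAP 6.2.2 names a Wilcoxon test on the change in fibre MSD without giving its variant or unit; if fibres are the unit, as the wording suggests, the nominal p-values are too small

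*SAP*

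**What the plan says.** SAP 6.2.2 obtains one MSD value for every fibre in the region of analysis of a slide: "These data are called the individual fiber MSD data". Each fibre is compared with a threshold, and for the endpoint itself "the average of the percent of positive fibers obtained in each slide will be computed" at each biopsy visit. The section then says "Key fiber MSD distribution statistics including the mean and the median will be summarized", and adds that a "non-parametric Wilcoxon test will be used to examine the change in fiber MSD distributions". That is all it says about the test. It does not say whether the test is paired, what the unit is, whether it runs within a participant or across a cohort, or how the nesting of fibres in slides, biopsies and participants is handled.

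SAP 5.1 sets the context: "There is no formal hypothesis testing in this study according to the original design of this FIH study". It expects significance only if the effect is dramatic, and continues: "Nominal p-values will be presented". SAP 5.2 and 6.2 plan bootstrap 95% confidence intervals for the secondary parameters. SAP 2.5 gives the cohort sizes as 3 (ambulatory low dose), 16 (ambulatory high dose) and 3 (non-ambulatory high dose).

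**The concern.** Fibres in one biopsy share a muscle site, a tissue section and a staining run, so they are not independent replicates of the treatment effect. A participant has one biopsy procedure per time point. A test on fibres therefore cannot separate a treatment effect from an ordinary difference between two biopsies, and with many fibres even a small difference gives a very small p-value.

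The documents give reason to expect such differences. SAP 6.2 restricts the tissue used in order to limit variability between sections of the same biopsy. SAP 6.2.2 takes the largest of the slide-level 95th percentiles at baseline, a step that has a purpose only if slides differ. Footnote n of the protocol's Schedule of Activities allows open or needle biopsies, and allows baseline tissue obtained outside the study.

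At stake is interpretation. A reader who has seen SAP 5.1 would take a small p-value as the sign of a dramatic effect, and it would appear beside the results for a secondary endpoint. Two programmers working from this one sentence could also report very different p-values.

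**Working it through.** **The plan's own figure.** There is none. The documents give no p-value, power or sample size for this test, so there is nothing to reproduce.

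**Which unit the wording implies.** SAP 3.2.1.2 speaks of the distribution of MSD over individual fibres within a participant. SAP 6.2.2 speaks of a baseline fibre MSD distribution for each slide, and of an overall one used to set the 99th-percentile threshold. In each case the distribution is over fibres. A test of change in such distributions most naturally compares fibre values.

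**Inputs.** The nominal level is taken as 0.05, matching the 95% intervals in SAP 5.2. The number of fibres per biopsy (m) and the between-biopsy intraclass correlation (ICC) are assumptions.

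**Formulas.** Design effect D = 1 + (m − 1) × ICC. Actual type I error ≈ 2 × [1 − Φ(1.96/√D)].

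| m | ICC | D | 1.96/√D | Type I error |
|---|---|---|---|---|
| 200 | 0.005 | 1 + 199 × 0.005 = 1.995 | 1.388 | 0.165 |
| 200 | 0.1 | 1 + 199 × 0.1 = 20.9 | 0.429 | 0.668 |
| 1,000 | 0.005 | 1 + 999 × 0.005 = 5.995 | 0.800 | 0.423 |
| 1,000 | 0.1 | 1 + 999 × 0.1 = 100.9 | 0.195 | 0.845 |

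**Check by simulation.** Data were generated with no true change, a random biopsy effect and a fibre residual, and a rank-sum test was run on the fibres.

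- At m = 1,000 and ICC 0.005 the error was 0.424 (formula 0.423).
- At m = 500 and ICC 0.05 it was 0.70 for one participant, 0.71 for 3 pooled and 0.66 for 16 pooled (formula 0.70). Pooling more participants does not cure the problem.
- At ICC 0 it was 0.04 to 0.07, about nominal.

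**Participant as the unit.** In the same simulations, a signed-rank test on the change in each participant's median, with 16 participants, had an error of 0.03 to 0.06 at every ICC tried.

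**Smallest attainable p.** For an exact two-sided signed-rank test this is 2/2ⁿ: 2/8 = 0.25 for n = 3, 0.0625 for n = 5, 0.031 for n = 6 and 0.00003 for n = 16.

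**The case against.** A reader might infer that the SAP commits to treating fibres as independent and that its p-values are therefore certain to be far too small. The text does not support that. It names no unit. The sentence just before the test concerns means and medians, and elsewhere in SAP 6.2.2 change means change from baseline summarised by cohort and visit. A paired signed-rank test on each participant's mean or median fits the wording, and on that reading there is no inflation. A figure beside the sentence is not readable in the public text, so a detail there cannot be excluded. This objection stands to the extent that the point must be conditional. It does not remove the point, because the fibre reading remains the more natural one and the SAP should not leave the choice open.

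A reader might also infer that this p-value will carry the evidence for transgene distribution. That goes beyond the documents. The immunofluorescence endpoints are percentages of positive fibres, averaged over slides at each visit, and the planned intervals are bootstrap intervals. Testing is declared not formal, and the dose-progression rules in protocol 3.5 do not use this test. All of this stands and limits the consequence.

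Finally, SAP 6.2.2 already shows data points instead of boxplots for cohorts of 3 or fewer. That is sensible, but it does not say whether a p-value would be given there.

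**Conclusion.** The specification is incomplete, and on its natural reading the test is invalid. If fibres are the unit, the nominal p-values are too small for any positive correlation within biopsies. The illustrative range of 17% to 85% depends on the fibre-level reading and on assumed values for the ICC (0.005 to 0.1) and the fibres per biopsy (200 to 1,000). The direction is firm, but the size cannot be derived from the documents. If participants are the unit, the p-values are sound in the cohort of up to 16 and uninformative in the cohorts of 3. Either way the text needs a clarification. Its importance is moderate: the test is supplementary and nominal, feeds no decision, and does not affect the percent-positive-fibre results.

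**What to change.** Amend the sentence in SAP 6.2.2 to state four things:

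- The participant is the unit of analysis.
- Each biopsy is reduced to one value, its mean or its median fibre MSD, with the choice fixed in advance.
- A Wilcoxon signed-rank test is applied to the participant-level changes from baseline in the ambulatory high-dose cohort, using those in the Pharmacodynamic Analysis Set. That set requires a baseline and a post-dose value, so n is at most 16 and may be lower.
- In the two cohorts of 3, individual values are shown with no p-value, and fibre-level distributions are kept as descriptive plots.

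The cost is a sentence or two in the SAP. No new data are needed. If fibres were the intended unit, the reported p-values become larger. If participants were intended all along, only the p-values in the cohorts of 3 are lost, and those could not have fallen below 0.25.

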6.2.3. Long-term safety

To evaluate the long-term safety of the study treatment, analysis of the primary safety endpoints described in Section 6.1 will include all data through 5 years post-treatment. These include the incidence, severity, causal relationship of TEAEs and clinically significant safety findings.

[figure not shown]

[figure not shown]

[figure not shown]

[figure not shown]

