8.1.4. Time Period for Collecting AE/SAE Information

The time period for actively eliciting and collecting AEs and SAEs ("active collection period") for each subject begins from the time the subject provides informed consent, which is obtained before the subject's participation in the study (ie, before undergoing any study-related procedure and/or receiving investigational product), through and including a minimum of 1 year following administration of the investigational product, also referred to as the Treatment Phase. In the Long-term Follow-up Phase (ie, Years 2 through 5), only SAEs and any AEs believed to be related to the investigational product will be reported.

For subjects who are screen failures, the active collection period ends when screen failure status is determined.

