8.1.4.1. Reporting SAEs to Pfizer Safety

All SAEs occurring in a subject during the active collection period are reported to Pfizer Safety on the CT SAE Report Form.

SAEs occurring in a subject after the active collection period has ended are reported to Pfizer Safety if the investigator becomes aware of them; at a minimum, all SAEs that the investigator believes have at least a reasonable possibility of being related to investigational product must be reported to Pfizer Safety.

Follow up by the investigator continues throughout and after the active collection period and until the event or its sequelae resolve or stabilize at a level acceptable to the investigator, and Pfizer concurs with that assessment.

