8.1.4.2. Recording Non-serious AEs and SAEs on the CRF

During the active collection period, both non-serious AEs and SAEs are recorded on the CRF.

Follow-up by the investigator may be required until the event or its sequelae resolve or stabilize at a level acceptable to the investigator, and Pfizer concurs with that assessment.

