3.1.1. Adverse Events

All nonserious AEs and SAEs occurring in a participant during the active collection period, which begins after obtaining informed consent will be recorded on the AE section of the CRF. MedDRA will be used to classify all AEs with respect to SOC and PT.

Relative to fordadistrogene movaparvovec administration:

Any AE that starts following start of treatment of fordadistrogene movaparvovec will be counted as treatment-emergent.

Events that occur in a non-treatment period (applies to screening until study drug administration only) will not be counted as treatment-emergent as this is a single period study.

Relative to sirolimus administration: Any AE that starts following start of treatment of sirolimus will be counted as treatment-emergent.

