3.2.2. Long-term safety

Incidence, severity and causal relationship of TEAEs and clinically significant safety findings, as described for the primary endpoints (above) through 5 years post-treatment.

Baseline is defined the same as those described in Section 3.1.

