6.1.1. Adverse Events

Incidence and severity of TEAEs will be reported.

Deaths and SAEs will be listed. The following will be summarized by dose cohort and ambulatory status at baseline:

- Incidence and severity of TEAEs (all causalities and treatment-related)
- Withdrawals due to TEAEs; and
- Incidence of SAEs (all causalities and treatment-related).

To evaluate the safety of sirolimus:

The incidence and severity of TEAEs (all causalities and treatment-related) relative to the initiation of treatment with sirolimus through 30 days post-last dose of sirolimus (approximately 44 days post-fordadistrogene movaparvovec infusion per sirolimus administration schedule) will be summarized for those participants who received sirolimus (sirolimus cohort) versus those who did not (non-sirolimus cohort).

No summaries will be provided by sirolimus cohort status since only one participant received sirolimus.

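### The 5-year all-causality TEAE summaries pool a period of full AE collection with Years 2-5, when unrelated non-serious events are out of scope, so counts by term, class and severity are biased downward or at best unbiased

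*SAP*

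**What the plan says.** **The endpoint.** Long-term safety is one of two secondary objectives. SAP 3.2.2 defines its endpoint as "Incidence, severity and causal relationship of TEAEs and clinically significant safety findings" through 5 years, in line with SAP 2.1 and Protocol Section 2.

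**The analysis.** SAP 6.2.3 states that "analysis of the primary safety endpoints described in Section 6.1 will include all data through 5 years post-treatment". Among the Section 6.1 summaries, SAP 6.1.1 lists TEAE incidence and severity, once for all causalities and once for treatment-related events, and SAE incidence on the same two bases. All are given by dose cohort and ambulatory status.

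**The TEAE definition.** SAP 3.1.1: "Any AE that starts following start of treatment of fordadistrogene movaparvovec will be counted as treatment-emergent". It sets no end date and no condition on seriousness or relatedness. The same section mentions the active collection period but does not say what happens after it.

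**The collection rule.** Protocol 8.1.4 sets active collection of AEs and SAEs from consent "through and including a minimum of 1 year following administration of the investigational product". For Years 2 to 5, "only SAEs and any AEs believed to be related to the investigational product will be reported". Protocol 8.1.4.2 adds: "During the active collection period, both non-serious AEs and SAEs are recorded on the CRF".

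**What is not there.** No visible SAP text splits the 5-year AE tables by collection period or tells the reader that collection changes. SAP 6.1 and 6.6 separate the 1-year from the 5-year analysis, but the latter is cumulative.

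**The concern.** A row in a 5-year all-causality table is read as 5-year incidence. Under Protocol 8.1.4, an unrelated non-serious event counts in that row only if it starts while full collection is running. The row therefore adds a full count for the early period to a filtered count for the rest, and does not estimate the stated endpoint for those events.

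The loss falls on the rows that a reader of long-term data would consult: preferred term, system organ class and severity. In this population it is not remote. Protocol 8.4.1 lists events expected to be common in DMD, such as loss of ambulation, muscle weakness, fracture and steroid-related metabolic change. Ambulatory participants enter at 4 to 12 years (Protocol 4.1), and wheelchair need is typical at 12 to 15 (Protocol 1.2.1), so some of these events can be expected in Years 2-5. Where they are judged non-serious and unrelated, the 8.1.4 rule leaves them out.

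**Working it through.** The plan gives no AE rate, precision target or bias figure for this endpoint, so there is no figure to reproduce. The check is a comparison of the texts followed by an illustration.

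**Step 1. Does the 8.1.4 rule govern the database or only expedited reporting?** The table in Protocol 8.1 sends no non-serious AE to the sponsor's safety group. A rule that keeps related non-serious AEs in Years 2-5 must therefore concern data collection, as its section heading says.

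**Step 2. Which rows does it reach?**

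| Event starting after full collection ends | Kept by Protocol 8.1.4? | Counted by SAP 3.1.1 and 6.2.3? |
|---|---|---|
| SAE, any causality | yes | yes |
| Non-serious, believed related | yes | yes |
| Non-serious, unrelated | no | yes, if it were recorded |

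Only the third line is lost. Captured counts cannot exceed true counts, so the bias is downward or zero.

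**Step 3. Share of the window.** Year 5 is Day 1825. Filtered collection covers at most (1825 − 365)/1825 = 1460/1825 = 80% of it. This is an upper limit, because 8.1.4 says a minimum of 1 year, and it is a share of time, not an estimate of bias.

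**Step 4. Share of unrelated non-serious events captured (assumed rates).** Let r be the Year 1 rate divided by the later annual rate, and c the fraction of these events that sites record in Years 2-5 anyway. Share captured = (r + 4c)/(r + 4).

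| | r = 1 | r = 2 | r = 5 | r = 10 |
|---|---|---|---|---|
| c = 0 (8.1.4 followed) | 1/5 = 20% | 2/6 = 33% | 5/9 = 56% | 10/14 = 71% |
| c = 0.5 | 3/5 = 60% | 4/6 = 67% | 7/9 = 78% | 12/14 = 86% |
| c = 1 | 100% | 100% | 100% | 100% |

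**Step 5. One preferred term at participant level (assumed).** Take a Year 1 risk of 0.10, a later annual risk of 0.10/r, c = 0, and everyone followed for 5 years. True incidence = 1 − 0.90 × (1 − 0.10/r)^4. Captured incidence = 0.10. Cohort sizes are from SAP 2.5.

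| | r = 1 | r = 2 | r = 5 | r = 10 |
|---|---|---|---|---|
| True 5-year incidence | 0.410 | 0.267 | 0.170 | 0.135 |
| Expected of all 22 (captured 22 × 0.10 = 2.2) | 9.0 | 5.9 | 3.7 | 3.0 |
| Expected of the 16 ambulatory high dose (captured 16 × 0.10 = 1.6) | 6.6 | 4.3 | 2.7 | 2.2 |

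In a cohort of 3, r = 1 gives 3 × 0.410 = 1.2 true against 0.3 captured.

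**Step 6. The any-TEAE row.** With a constant rate λ per participant-year and no later event serious or related, true 5-year incidence is 1 − exp(−5λ) and captured incidence is 1 − exp(−λ). At λ = 0.2 this is 63.2% against 18.1%. At λ = 3 it is 100% against 95.0%, or 22.0 against 20.9 of 22. If most participants have some TEAE in Year 1, this row loses little.

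**The case against.** **Much of the remedy is already planned.** The 1-year all-causality analysis is the primary safety analysis, and SAP 6.1.1 already lists SAE and treatment-related summaries. The study is descriptive, and nothing here bears on dose progression or stopping. This stands, and it limits the weight of the point. It does not remove the pooled 5-year all-causality rows or the missing note on collection.

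**All data may simply mean all data collected.** On that reading the table is accurate about the database, but it still does not give the endpoint, which is TEAE incidence through 5 years.

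**Sites may record more than 8.1.4 asks.** Protocol 7.2.11 has any adverse event from a wellness check-in entered on the CRF, and such check-ins continue in long-term follow-up. If every site recorded everything, c = 1 and there is no bias. The bias is therefore conditional on sites following 8.1.4, and mixed practice would give counts that depend on the site.

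Three stronger readings are tempting, and the documents do not support them:

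- *The 5-year SAE counts are incomplete too.* Protocol 8.1.4.1 says that "SAEs occurring in a subject after the active collection period has ended are reported to Pfizer Safety if the investigator becomes aware of them". That section is about the safety report form, a separate channel from the CRF. Section 8.1.4 expressly keeps SAEs in scope for Years 2-5, and the 8.1 table has all SAEs on the CRF. Section 8.1.4.2 says what is recorded in the active period and does not bar later recording. This calls for confirmation; it does not show a loss.
- *The protocol contradicts itself throughout on long-term AE recording.* The Schedule of Activities row for AE monitoring and the Section 6.12 check-ins set no recording rule; they are how a site would learn of SAEs and related AEs. The sentence in Section 8.1 about reporting all events defers to the paragraphs that follow it, which include 8.1.4. The real tensions are with 7.2.11 and, for unrelated non-serious events, with 8.4.1, which says the listed events should still be recorded as AEs.
- *The plan overstates the related share of events.* A reader might form that ratio from adjacent tables, but no visible SAP text plans it.

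**Conclusion.** The mismatch is certain on the text: SAP 6.2.3 with 6.1.1 and 3.1.1 asks for all-causality TEAE summaries over 5 years, while Protocol 8.1.4 does not collect unrelated non-serious AEs for all of that time. If sites follow 8.1.4, the pooled all-causality counts by preferred term, system organ class and severity are too low or, at best, unbiased.

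The size cannot be derived. The capture shares of 20% to 71% and the expected counts in the tables rest on assumed values of the rate ratio, the recorded fraction and the Year 1 risk, and the participant counts also assume complete follow-up. A reader might infer that every 5-year row is unreliable. That goes too far: under this rule the 1-year primary analysis, the treatment-related rows and the SAE rows are intact, and the any-TEAE row may hardly move. The point should be fixed before the 5-year tables are produced, but it does not touch the primary objective.

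**What to change.** 1. In SAP 6.2.3 and 3.2.2, report all-causality TEAE incidence and severity for the full-collection period only. Report Years 2-5 separately as SAEs (all causalities) and treatment-related AEs. Give the number of participants still followed in each period.
2. If a pooled 5-year all-causality table is kept to match the endpoint wording, footnote the change in collection and do not label it as 5-year incidence of all TEAEs.
3. In the protocol, reconcile Section 8.1.4 with Section 7.2.11 on check-in events and with Section 8.4.1 on unrelated non-serious protocol-specified events. Confirm that Section 8.1.4.2 does not end CRF recording of SAEs after Year 1.

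The cost is SAP wording, one table split or footnote, and one protocol clarification. No new data are needed. Protocol Section 9 allows the SAP to modify planned analyses and calls for an amendment only for major changes to the primary endpoints or their analyses, which this is not. The downside is a narrower 5-year AE presentation: it would no longer offer a single all-causality incidence for the whole period.
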